Participants who complete the 18 month visit prior to the approval of pertinent forms (i.e., Transfer of Dog Ownership Verification form, Dog Ownership Chip Registry Instructions form and VA Certificate of Study Completion [dog retention version], etc.) can be provided with a copy of these forms upon request.

- **Veterinarian checks**

Participants must take their dogs to a Veterinarian, as follows:

- Week 1 (\pm 14 days) after receiving a dog, at which a dog parasite check will be conducted. Veterinary Checklist packet (includes form 23) can be provided at the Home Clearing Visit or Week 1 visit.
- Month 6 (\pm 28 days) after receiving a dog, at which a dog parasite check will be conducted. Veterinary Checklist packet (includes form 23) will be provided at the Month 03 visit.

- Month 12 (\pm 28 days) after receiving a dog, at which an annual comprehensive wellness examination will be conducted. This will require assessment of the dog's weight, major body systems and teeth, the dog will be checked for internal and external parasites, the dog will have a tooth cleaning and will receive vaccinations for canine communicable diseases. Veterinary Checklist packet (includes form 23) will be provided at the Month 09 visit.
- Month 17 (\pm 28 days) after receiving a dog, at which a dog parasite check will be conducted. Veterinary Checklist packet (includes form 23) will be provided at the Month 15 visit and required prior to completion of the Month 18 visit.
 - Completion of this parasite check is a prerequisite for keeping the dog at the end of the study.

The participant will be provided with a Veterinary Checklist packet that includes a cover letter, contact sheet, the Veterinary Checklist, and a postage paid envelope during the designed visits above. The participant will be instructed to schedule each veterinary check and will be responsible for giving the checklist, contact sheet, and postage paid envelope to the selected Veterinarian. Options for returning the Veterinary Checklist include, a) Veterinarian can give the completed form to the participant in order for the participant to return it directly to the study team; b) Veterinarian can fax the completed form to the study team; and, c) Veterinarian can mail the form to the study team using the self addressed stamped envelope. A VA veterinarian will review each Veterinary Checklist and follow up as needed if dog health problems are noted.

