Relatedness involves an assessment of the degree of causality (attributability) between the study intervention and the event. The assessment provided by the site investigator is part of the information used by the sponsor to determine if the adverse event presents a participant safety concern. Pursuant to CSP Global SOP 3.6, an AE is deemed to be associated with the use of a study intervention if "[t]here is a reasonable possibility that the experience may have been caused by the intervention or by participation in the trial." Thus, all adverse events with a reasonable causal relationship to the study intervention should be considered "related". A definite relationship does not need to be established. The following levels of relatedness will be used in this trial:

- Not attributed to a study intervention (study dog)
- Possibly attributed to a study intervention (study dog)
- Attributed to a study intervention (study dog)

Only possibly related or related events must be reported on a study form.

2. Adverse Event Definitions for Animals

The USDA Animal Welfare Act Regulations (AWAR) and Public Health Service Policy on the Care and Use of Animals in Research ("PHS Policy") govern animal research involving dogs. All VA-funded animal research must also comply with the rules and policies utilized by the accrediting body for animal research, which is the Association for Assessment and Accreditation of Laboratory Animal Care (AAALAC). VA policy incorporating these federal and accrediting standards is found in ORD Handbook 1200.07, Use of Animals in Research (11/23/2011), and ORO Handbook 1058.01, Research Compliance Reporting Requirements (11/15/2011; primarily paragraph 8).

Cumulative reporting requirements for IACUCs are found in VHA Handbook 1200.07, item 8.i, which lists the following categories of reportable deficiencies applicable to this study. These include (a) serious or continuing non-compliance with PHS Policy (including any serious deviation or continuing non-compliance with the provisions of the Guide, as required by the PHS Policy) or USDA AWAR, and (b) suspensions of protocols previously approved or suspensions of procedures or studies never given approval.

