As federal regulations and VA policy apply to this study, each site IACUC will be required to monitor the dogs enrolled at that site. Site IACUC's will ensure that (a) the dogs are used according to the protocol approved by the IACUC, (b) that the dogs receive appropriate veterinary care as needed, (c) not more than the approved number of dogs are used, and (d) that the dogs do not pose a health (e.g., zoonotic parasites) or safety (e.g., biting) risk to people or

other animals that are around them. If the IACUC finds that any of these expectations have not been met, then they must investigate the matter, determine if corrective actions are needed, report the non-compliance if the matter qualifies, and monitor the corrective actions to make sure the issue is resolved and that proper measures are in place to prevent recurrence of the problem.

The term “adverse event” is not defined for animal research issues, but the following shall be considered an AE for the purposes of this study, and deemed reportable:

1. Bites of any level according to the Dunbar dog bite scale ([http://www.apdt.com/veterinary/assets/pdf/Ian Dunbar Dog Bite Scale.pdf](http://www.apdt.com/veterinary/assets/pdf/Ian_Dunbar_Dog_Bite_Scale.pdf)). The scale ranges from obnoxious or aggressive behavior but no skin contact by the dog’s teeth (Level 1) to slight bleeding caused by a tooth laceration without a puncture (Level 2) to increasingly deep tooth punctures of the skin (Levels 3 and 4) to multiple Level 3 or 4 bites (Level 5) to death (Level 6).
2. Any herding or similar aggressive behavior toward children. In experience, such dominance behavior is a precursor to biting incidents.
3. Diagnosis of any zoonotic parasitic or other disease in the participant, participant’s family, or in people with regular contact with the dog. This would include intestinal parasites such as hookworms, roundworms, and giardia, as well as bacterial diseases such as salmonellosis or leptospirosis. It would also include fungal infection of the skin such as ringworm.
4. Unprovoked aggression against other dogs or cats.
5. Aggression of any kind toward people who are exposed to the dog under any environment. This does not imply that there are no circumstances in which aggression might be acceptable (e.g., physical attack by a person or dog on a participant or another person would be warranted), but the matter should be reported and investigated.

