6. Any indication that a dog is being mistreated in the home environment by any member of the household.
7. Repeated refusal by the participant to go to routine veterinary visits, or decisions not to seek veterinary treatment for dog injuries or significant illnesses.
8. Diagnosis of chronic illness, hip or elbow dysplasia, or a genetic condition refractory to treatment that will likely reduce the working life of a Service Dog or the ability of an Emotional Support Dog to be a potentially positive factor on the participant.

- **Adverse Event Follow-Up**

For each reported AE, site investigators follow up with participants until the event resolves and ensure that appropriate care is provided, but there is no case report form to fill for AE follow-up.

Adverse events must be reported as Serious Adverse Events (SAE) if they meet the SAE reporting requirements described below.

- **Serious Adverse Events**

1. Definition of Serious Adverse Event (SAE)

Serious adverse events are defined by the ICH for Clinical Safety Data Management and CSP Global SOP 3.6.2, as any untoward medical occurrence that:

- Results in death,
- Is life threatening,
- Requires inpatient hospitalization or prolongation of existing hospitalization,
- Results in persistent or significant disability or incapacity,
- Is a congenital anomaly/birth defect, or
- Any other condition that, based upon medical judgment, may jeopardize the subject and require medical, surgical, behavioral, social or other intervention to prevent such an outcome.

Any adverse event that meets the definition of “Serious” will be reported on an SAE Form. All SAEs will be classified as either “related,” “possibly related,” or “not related” to study intervention. A definite causal relationship does not need to be established.

2. Serious Adverse Event Monitoring

Participants will be monitored for SAEs at each study visit and during any contact with the participant. Each serious adverse event is reported on an SAE Form. Active monitoring for SAEs begins at the time the Informed Consent Form is signed and continues until the earlier of the 30 days after the participant’s completion, early termination of study participation, or the end of the study. The final SAE monitoring review can be completed by a chart review. The date study participation ends is entered on the Study Completion/Termination Form. Safety data from the pre-randomization and post-pairing periods will be analyzed separately.

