- **Reporting Adverse Events and Serious Adverse Events to the Study DMC and other Oversight Bodies**

The CSPCRPCC is responsible, in conjunction with the CSPCC, for coding study safety data into the MedDRA (Medical Dictionary for Regulatory Affairs) Dictionary and creating event tabulations. The study biostatistician will present a summary of those events to the data monitoring committee (DMC) on a schedule set by the DMC. The DMC will recommend to the CSR Director whether the study should continue or be stopped for safety reasons. Summary reports from the DMC will be provided to each site for their records.

Unexpected AEs and SAEs will be reported to the Study Chairs' Office. The Study Chairs and the CSPCC Directors will report SAEs that are determined to be both related to the investigative treatment and unexpected to the CSR Director and site investigators after review.

- **Reporting Adverse Events and Serious Adverse Events to the IACUC**

The site investigators will report all SAEs and Unanticipated Problems involving risks to animals to their individual site IACUC committee and to the Chief Veterinarian Medical Officer.

The AE Specialist at the CSPCRPCC will address questions about managing or reporting of adverse events or serious adverse events.

- **Additional Safety Concerns**

1. Unmasking the study treatment

The study treatment is not blinded, thus unmasking is not applicable in this protocol.

2. Discontinuation of treatment (removal of dog)

A participant may be terminated from the study. If so, the dog will be removed. Medical and scientific judgment should be exercised in deciding whether to terminate a participant from the study. Before any paired participant is terminated, the site investigator must contact the study chair for instructions and approval. A participant may be terminated and the dog removed from a participant if:

- a. Participant does not keep scheduled study visits and does not respond to phone calls or attempt to reschedule appointments. See Lost to Follow-Up section for additional details.
- b. Participant moves so far away that the study team cannot practically continue to make home visits
- c. Participant is deployed
- d. Participant withdraws from study and chooses to return dog
- e. There is evidence that the dog has been physically or psychologically abused or mistreated
- f. There is evidence that the participant is failing to keep the dog healthy
- g. Participant has not maintained mental health treatment

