## 8 ADVERSE EVENTS

An Adverse Event (AE) can be any unfavorable or unintended sign (including an abnormal laboratory finding), symptom, or disease temporally associated with the study interventions. For the purposes of this study, the study interventions are 1) being paired with a Service Dog and 2) being paired with an Emotional Support Dog. In this study, information on AEs related to or possibly related to study intervention, for the participant, participant family members or the study dog, and on all serious adverse events (SAEs) will be collected and recorded.

Adverse events will be recorded during screening, observation phase and during the 18 months of follow-up. The reporting period for AEs begins when the participant signs the informed consent form and continues until the earlier of the 30 days after the participant's completion or early termination of study participation or the end of the study. All adverse events with a reasonable causal relationship to the study intervention should be considered "related". A definite relationship does not need to be established. The following levels of relatedness will be used in this trial:

- Not attributed to a study intervention (study dog)
- Possibly attributed to a study intervention (study dog)
- Attributed to a study intervention (study dog)

Only possibly related or related events must be reported on a study form.

Incidence of adverse events will be summarized for each treatment group by body system and MedDRA term. The number and percentage of participants with each body system and MedDRA term will be presented for each treatment group. Tables to summarize the incidence rates will be created for each of the following groups:

- Adverse events
- Adverse events by relationship to treatment
- Adverse events leading to premature discontinuation
- Adverse events presented in descending order of frequency by MedDRA term (no System Organ Class shown)
- Serious adverse events
- Serious adverse events by type
- Serious adverse events by relationship to treatment

Adverse events that led to premature discontinuation from the study will be listed. Serious adverse events will also be listed. These listings will contain details about the adverse event such as intensity and relationship to study treatment. All adverse events will be coded with MedDRA (updated version).

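### Item 8 of the dog adverse event list uses a different reporting criterion for each dog type, so by-arm counts of dog illness are not like-for-like

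*Protocol*

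**What the plan says.** Protocol XIII, Adverse Event Definitions for Animals, introduces a list of eight items by saying that "the following shall be considered an AE for the purposes of this study, and deemed reportable". Items 1 to 7 cover bites, herding or similar behaviour toward children, zoonotic disease in people, aggression toward other animals, aggression toward people, mistreatment of the dog, and missed veterinary care. None of them refers to the type of dog.

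Item 8 does. It names three kinds of diagnosis in the dog (a long-term illness, dysplasia of a hip or elbow, and a genetic condition that resists treatment), and its qualifying clause reads: "will likely reduce the working life of a Service Dog or the ability of an Emotional Support Dog to be a potentially positive factor".

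Four other places bear on how item 8 works:

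- **Detection.** Protocol X, Veterinarian checks, sets one schedule for all study dogs (week 1 and months 6, 12 and 17) and adds that "A VA veterinarian will review each Veterinary Checklist and follow up as needed if dog health problems are noted".
- **Masking.** Protocol XIII, Additional Safety Concerns, states: "The study treatment is not blinded, thus unmasking is not applicable in this protocol". Protocol VIII and SAP 3.4 show that site and participant learn the assignment once the Home Clearing visit is complete.
- **Relatedness.** The same rule applies to both arms: "Only possibly related or related events must be reported on a study form". SAP 8 repeats it.
- **Analysis.** SAP 8 includes the study dog among those whose adverse events are collected and then says "Incidence of adverse events will be summarized for each treatment group by body system and MedDRA term". The tables count participants, and no test is described. SAP 5.5.1.1 says the DMC will use adverse event and serious adverse event data to judge whether the trial should terminate.

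**The concern.** A harm definition used in a by-arm table should give the same answer for the same diagnosis in either arm. Item 8 instead asks whether the illness impairs the role the dog was assigned, and the role is what was randomised. A Service Dog has five trained tasks, some of them physical (Protocol IX). An Emotional Support Dog has no trained disability task and gives companionship. A lasting joint or medical condition could end task work and leave companionship intact. Such a dog would count in one arm and not in the other.

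At stake is how dog-illness counts in the safety reports are read. Dogs in both arms come from the same vendors and breeds (Protocol I) and face common medical standards (Protocol IX). A reader who sees a by-arm difference under item 8 could not tell whether it reflects the dogs or the definition.

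**Working it through.** The documents give no dog-illness rate, so there is no planned figure to reproduce. The check is mainly textual, followed by a short formula.

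**1. Compare the items.** Items 1 to 7 apply to any study dog. Item 8 has two tests, working life for one dog type and capacity to be a positive factor for the other. Nothing in the Protocol or SAP makes the tests equivalent.

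**2. Read the sentence both ways.** The qualifying clause can attach in two places.

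- *Broad reading:* it qualifies all three diagnosis groups, so chronic illness, dysplasia and refractory genetic conditions all face the arm-specific test.
- *Narrow reading:* it qualifies only the genetic condition. Chronic illness and dysplasia are then reportable in both arms without condition.

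On either reading one diagnosis can qualify in one arm only. On the narrow reading that is confined to genetic conditions.

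**3. Ask who judges.** The criterion cannot be applied without knowing the dog type, so the judgement is unmasked by construction.

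**4. Look for a step that equalises the tests.** The veterinary schedule and review are the same in both arms, which equalises detection but not reporting. The relatedness rule has the same wording for both arms, but it sits beside item 8 and does not replace its two tests.

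**5. Formula.** Let r be the true diagnosis rate, assumed equal in the arms. Let mS and mE be the shares of diagnoses that fall below the Service Dog and Emotional Support Dog thresholds.

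- Reported rates: r(1 − mS) and r(1 − mE).
- Ratio, Service Dog to Emotional Support Dog: (1 − mS)/(1 − mE).
- Expected difference in reports with n dogs per arm: n × r × (mE − mS).

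The planned n is 110 per arm (Protocol XVIII, Sample Size: 82/(1 − 0.25) = 109.3, rounded up to 110). The documents do not give r, mS or mE. The values below are assumptions that show how the formula behaves; they are not estimates.

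| mS | mE | Ratio |
|---|---|---|
| any value below 1 | same value | 1.0 |
| 0.25 | 0.50 | 0.75/0.50 = 1.5 |
| 0.50 | 0.25 | 0.50/0.75 = 0.67 |

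With a gap of 0.25 between the shares and an assumed r of 2% to 10%, the expected difference is 110 × 0.02 × 0.25 = 0.55 to 110 × 0.10 × 0.25 = 2.75 reports. The ratio can lie on either side of 1, and the counts are small.

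**The case against.** The best case on the other side has five parts.

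- **Ambiguity.** If the clause attaches only to genetic conditions, the obvious examples (mild dysplasia, a manageable chronic illness) are reportable in both arms. This stands as a limit on scope. It is also a reason to reword, since sites could read the sentence differently.
- **Direction.** Both tests ask whether the illness harms the dog's role. The Emotional Support Dog test is vague enough that a condition might meet it without shortening a working life. This stands. The task difference makes more Service Dog reports likelier, but that is inference.
- **Frequency.** Dogs are evaluated at 16 to 24 months of age and must pass hip, elbow and general health screening (Protocol IX), so diagnoses may be few. This stands.
- **Use.** SAP 8 is descriptive, counts participants, and does not say how Form 26a events enter its tables. No study objective concerns dog health. This stands, although a descriptive table still reaches the DMC.
- **Recoverability.** A VA veterinarian already reviews checklists from both arms, so a like-for-like count might be rebuilt. This is largely right, but nothing in the plan says it will be done.

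A reader might go further and infer that the rule must inflate illness counts for Service Dogs, and so bias the trial's safety comparison or its policy conclusion. The documents do not support that. Service Dog diagnoses must also pass a test, so the two under-reporting shares could be equal or reversed, and no planned analysis is shown to turn on this event class.

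**Conclusion.** The point holds as a defect of definition. Item 8 alone among the eight items depends on dog type, it is judged by people who know the arm, and study-dog events are collected under an adverse event plan that summarises by arm. Counts of this event class are not like-for-like and could be distorted.

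Neither the size nor the direction can be stated. The formula assumes equal true incidence, which the common vendors, breeds and medical standards make reasonable but do not prove. Distortion is absent if the two below-threshold shares are equal. Scope is limited to one of eight dog event items, and on the narrow reading to genetic conditions within it. Definitions for participant events, bites, aggression, zoonoses and deaths are untouched. This is a modest weakness, worth correcting because the correction is cheap.

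**What to change.** 1. Reword item 8 as one criterion that is identical for both dog types, and list the diagnoses it covers so that the reach of any qualifier is clear. If a threshold of seriousness is wanted, use the same one for every study dog.
2. Record the likely effect on the dog's role (working life or companionship) as a separate field on Form 26a. This keeps the information item 8 now seeks.
3. Identify diagnoses from the Veterinary Checklists already completed on the same schedule in both arms. The checklist form is not in the documents and three of the four checks are described as parasite checks, so confirm that it records these diagnoses.
4. State in SAP 8 that Form 26a events are tabulated by arm on the arm-neutral count.

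The cost is a wording change, one form field, one sentence in the SAP and a few more dog adverse event forms.

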The International Conference on Harmonization (ICH) defines adverse events (AEs) for Clinical Safety Data Management (ICH-E2A) as “any untoward medical occurrence in a clinical investigation subject that is subjected to one of the study treatments that do not necessarily have to have a causal relationship with the treatments. An AE, therefore, can be any unfavorable or unintended sign (including an abnormal laboratory finding), symptom, or disease temporally associated with the study interventions.”

For the purposes of this study, the study interventions are: a) being paired with a Service Dog and b) being paired with an Emotional Support Dog.

In this study, information on AEs related to or possibly related to study intervention for the participant, participant family members, or the study dog, and on all serious adverse events (SAEs) will be collected and recorded. See the section below on “Relatedness”. A separate section below describes the collection of safety information for SAEs.

The reporting period for AEs begins when the participant signs the informed consent form and continues until 30 days after: the participant’s completion, early termination of study participation, or the end of the study (whichever comes earlier). Each related/possibly related AE will be reported to the Sponsor, the VA Cooperative Studies Program, including any increase in frequency or severity of a condition that was present prior to the start of the study. During the study, adverse events can be spontaneously reported or elicited during open-ended questioning, examination, or evaluation of the participant at study visits.

Related or possibly related adverse events not meeting the criteria for an SAE (see below) must be recorded on the Adverse Event Form. (Those that meet SAE criteria are documented on the SAE Form.) One form should be completed for each AE reported. Adverse events should be reported in sequential order as they occur and submitted with the other case report forms for the participant's visit.

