3. Expedited Reporting of Serious Adverse Events

All SAEs require prompt reporting to the CSP Coordinating Center and CSP Clinical Research Pharmacy Coordinating Center (CSPCRPCC) within 72 hours of the site investigator becoming aware of the event. The Adverse Event (AE) Specialist at the CSPCRPCC is responsible for evaluating all SAEs for participant safety concerns and regulatory reporting. The AE Specialist will consult with the Chairman’s office during the review process, as necessary.

* Because of the high profile of this study, certain SAEs must be reported to the sponsor within 12 hours of the site investigator being made aware of the event. **These events include any dog deaths, dog bites, or participant deaths.**

CSPCRPCC maintains a database of serious events for evaluation, by using the Medical Dictionary for Regulatory Activities (MedDRA) for coding and trending. Periodic summaries will be provided to the Data Monitoring Committee, the Study Chairman's office and Executive Committee (as necessary). Events that are determined to be serious, unexpected, and related to the study treatments will be reported to the site investigators, Chair's office, and to the VA Cooperative Studies Program Central Office. CIRB policy will likely mirror these reporting requirements so it is important to review and understand these requirements as well. The CIRB website provides a number of resources related to current CIRB policy and SOPs.

SAE Forms will be sent to the Perry Point CSPCC as directed. The CSPCRPCC will also have access to the information on the SAE Forms.

4. SAE Follow-up Reporting

If additional information is require the CSPCC or CSPCRPCC will fax or email a request to the site personnel reporting the SAE. The site should handle requests for SAE follow-up information in the same prompt manner that original SAE reports are handled. Serious adverse events should be followed to resolution, stabilization, or the end of the study, whichever occurs first. If an SAE is still ongoing by the time the SAE Form is submitted to the Perry Point CSPCC, complete an SAE Follow-up Form every 30 days until the SAE is resolved or stabilized. SAE Follow-up Forms will be sent to the Perry Point CSPCC.

- **Reporting Adverse Events and Serious Adverse Events to the VA Central IRB**

It is the responsibility of the site investigator / coordinator at each participating site to know and comply with the AE and SAE reporting requirements of the VA CIRB.

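### The protocol does not say which dog bites are serious adverse events, so the form used and the SAE counts by arm can vary with how a site reads Section XIII

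*Protocol*

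**What the plan says.** Four parts of protocol Section XIII, and one list under Risks to subject, bear on how a bite is recorded.

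- **Expedited Reporting of Serious Adverse Events.** SAEs in general go to the coordinating centers within 72 hours. Then: "certain SAEs must be reported to the sponsor within 12 hours of the site investigator being made aware of the event". The next sentence reads: "These events include any dog deaths, dog bites, or participant deaths". No Dunbar level or seriousness condition is attached.
- **Adverse Event Definitions for Animals.** The list opens with "the following shall be considered an AE for the purposes of this study, and deemed reportable". Item 1 is "Bites of any level according to the Dunbar dog bite scale". The bottom of that scale, Level 1, is "obnoxious or aggressive behavior but no skin contact" by the teeth. Item 5 separately covers aggression toward people.
- **Adverse Events.** Related or possibly related events that miss the SAE criteria go on the AE Form: "Adverse events should be reported in sequential order as they occur and submitted with the other case report forms" for the visit.
- **Adverse Event Follow-Up and the SAE definition.** "Adverse events must be reported as Serious Adverse Events (SAE) if they meet the SAE reporting requirements described below". The criteria are death, threat to life, hospitalization, disability, congenital anomaly, and a medical-judgment category. Bites are not mentioned.
- **Risks to subject.** After any bite, a list of people must be told immediately. The AE or SAE status of the bite is not given.

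SAP Section 8 tabulates AEs and SAEs by treatment group, body system and MedDRA term. It has no row for bites.

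**The concern.** A bite that breaks no skin, or barely does, will often miss the SAE criteria. A coordinator who takes the 12-hour passage literally files it as an SAE. A coordinator who works from the definitions and the criteria files it as an AE with the visit forms. Both have followed the protocol.

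The choice has practical consequences. SAE status brings entry in the serious-events database and a follow-up form every 30 days while the event continues; for AEs there is no follow-up case report form. SAEs involving risk to animals go to the site animal care committee and the Chief Veterinarian Medical Officer. SAE status also decides which SAP Section 8 table holds the event.

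Bites are a known safety concern here: protocol Section II (Enrollment Holds) says the pilot was stopped after two bites and a dog death. Protocol Section XVIII (Criteria for Study Termination) and SAP 5.5.1.1 name safety data, including AEs and SAEs, as what the DMC will use to decide on termination. An SAE count that mixes no-contact events with serious injuries at one site, and excludes the former at another, is hard to interpret for that purpose.

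**Working it through.** The plan states no bite or SAE rate, so there is no figure of its own to reproduce. The check is mainly a comparison of the passages.

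**Step 1: follow one event through the text.** Take a Level 2 bite (slight bleeding, no puncture) that the investigator judges not to meet any SAE criterion.

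| Question | Reading A: every bite is an SAE | Reading B: only bites already meeting the SAE criteria get the 12-hour clock |
|---|---|---|
| Textual basis | 12-hour passage names bites without condition | AE definitions, AE form rule, and the rule linking AE to SAE |
| Form | SAE Form | AE Form |
| Time limit for the form or report | 12 hours to the sponsor | With the visit's case report forms |
| Follow-up form | Every 30 days until resolved or stable | None |
| SAP Section 8 | Counted in the AE and SAE tables, or the SAE tables only | AE tables only |
| Reportable at all | Yes | Yes |

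**Step 2: look for a tie-breaker.** The linking rule in Adverse Event Follow-Up favors B. The unconditional wording of the 12-hour passage favors A. Risks to subject covers notification only. The SAP form tables list AE and SAE forms for participants and for dogs (26, 26a, 27, 27a), but neither document says which takes a bite. Nothing decides.

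**Step 3: what moves and what does not.** Every bite is reportable under both readings, so the total of reportable events is fixed. The AE/SAE split moves. Within the AE list, a Level 1 event fits item 1 (bite) and item 5 (aggression toward people), so its label can move too, but it is a reportable AE under either item.

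**Step 4: illustration of scale, on assumed rates.** The inputs are 110 participants per arm (protocol, Sample Size: 82 / (1 − 0.25) = 109.3, rounded up to 110), an assumed proportion r with a bite of any level, and an assumed share s of bites meeting the SAE criteria.

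Reading A: 110 × r. Reading B: 110 × r × s, with s from 0 to 0.25.

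| r | A: bite SAEs per arm | B: bite SAEs per arm |
|---|---|---|
| 2% | 2.2 | 0 to 0.55 |
| 5% | 5.5 | 0 to 1.38 |
| 10% | 11.0 | 0 to 2.75 |
| 20% | 22.0 | 0 to 5.5 |

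The ratio A to B is 1/s, so at least fourfold over this range of s. That follows from the assumed share and is not evidence about this trial.

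**The case against.** The best reply is that the passages do not contradict each other. The linking rule says when an AE becomes an SAE, and the phrase about certain SAEs can mean a subset of events that are already serious and get a shorter clock. The protocol also names an AE Specialist to answer reporting questions. This stands in part: the defect is an ambiguity and not a flat contradiction. It does not remove the problem, because the 12-hour sentence supports the other reading equally well.

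Other safeguards also stand. Any bite must be notified immediately under Risks to subject. SAP 5.5.1 gives the DMC AE data, SAE data and dog behavior, and lets it ask for further tables.

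Several stronger conclusions are tempting, and the documents do not support them:

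- **That oversight of bites is delayed.** Setting 12 hours against a quarterly visit compares sponsor notification with form submission. Immediate notice of any bite is required either way, and the recipients' details were removed from the text reviewed.
- **That a site's reading creates a difference between arms.** A site that reads the passage one way does so for both of its arms. That can scale counts; no mechanism for creating a difference is shown.
- **That AE and SAE data are the DMC's only ground for stopping.** Protocol Section XIX (Monitoring bodies) and SAP 5.5.1 keep others, such as poor intake and treatment differences.
- **That the pilot gives the number of affected events.** Two bites over 22 pairings (13 + 9) mixes bites from before January 2012 with a later status count. The bite levels are not given, the bites are not said to come from separate pairings, and all pilot pairings were with Service Dogs.

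**Conclusion.** The point holds as an unresolved ambiguity that should be corrected. The protocol does not say which bites are SAEs, or whether the 12-hour clock applies regardless of seriousness. As a result, the form, the SAE follow-up, the SAE reporting on animals and the SAE counts by arm can differ between compliant sites. The total of reportable events is unaffected, apart from a possible change of label for Level 1 events, and the primary efficacy analysis is not touched.

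The size cannot be derived from the documents. Under the assumptions in the illustration, bite SAEs per arm could differ fourfold or more between the readings. This rests on most bites missing the SAE criteria, which is plausible at the low end of the Dunbar scale but is not stated in the plan.

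**What to change.** Reconcile the parts of protocol Section XIII so that notification and seriousness are separate questions:

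1. State whether the 12-hour notice applies to every bite, serious or not, and how it relates to the immediate notice under Risks to subject.
2. State that SAE status follows only the listed SAE criteria. If the sponsor intends every bite to be an SAE, say so in the animal definitions and in the SAE definition instead. That choice is the sponsor's.
3. Place Level 1 events under item 1 or item 5, not both, and name the form that takes a bite.
4. In SAP Section 8, add a tabulation of bites by Dunbar level and arm, whichever form they were filed on.

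The cost is a few sentences and one table entry, plus a field for Dunbar level if the forms lack one; their fields are not shown in the documents. If SAE status follows the criteria alone, bites that miss them leave the SAE count, and readers must look to the bite entry.
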